9.4.4. Safety Analyses

All safety analyses will be presented using the safety analysis set. Inferential analyses will generally not be performed for safety endpoints unless specified in the SAP. Frequency and percentage will be presented for categorical variables. Sample size, mean, standard deviation, median, interquartile range, and range will be presented for continuous variables.

9.4.4.1. Adverse Events

Treatment-emergent AEs (TEAEs) are those that begin on or after the date of the first dose of study intervention and on or before 42 days after the start of the last cycle of study intervention.

Summaries (number and percent of participants) of TEAEs (by system organ class and preferred term) will be provided as follows:

- All
- Severe, life-threatening, and fatal

- Treatment-related
- Severe, life-threatening, and fatal treatment-related
- Serious
- Treatment-related serious
- Those leading to study intervention discontinuation
- Those leading to study intervention interruption
- Fatal

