- Without underlying bundle branch block:
 - Interrupt for QTc >500 msec OR uncorrected QT >600 msec
 - With underlying bundle branch block:
 - If baseline QTc <450 msec, then interrupt for QTc >500 msec
 - If baseline QTc 450 to 480 msec, then interrupt for QTc >530 msec

In the event of prolonged QTc, the participant should also be assessed for other medications that may impact QT interval, with any necessary changes made to concomitant medications. Infusion of study intervention may be resumed once QTc is <480 msec. Following resumption of infusion, ECGs are to be checked daily until the participant has had 3 consecutive (daily) tracings with QTc <480 msec, after which follow-up ECGs will be as per institutional standard of care.

Bilirubin: If total bilirubin is >2 mg/dL, refer to the daunorubicin/idarubicin product label for dosage adjustments. No adjustment to the study intervention dosing is recommended.

Anticoagulant therapy: If a participant requires short-term anticoagulant therapy, interrupt the administration of study intervention. Infusions may be resumed if anticoagulant therapy is discontinued and aPTT is <35 seconds.

Note: If study intervention is interrupted and not restarted during the same treatment cycle, the participant may receive study intervention (bolus and infusion) during the next treatment cycle (assuming the participant no longer meets any of the interruption criteria).

Criteria for Evaluation

Induction and consolidation treatments are administered as *cycles*. A complete treatment cycle consists of the administration of therapy (i.e., chemotherapy with cytarabine \pm anthracycline plus blinded study intervention) and all scheduled assessments to evaluate the response to treatment, including bone marrow and hematologic recovery. The complete duration of a treatment cycle is dependent on the individual participant's response to treatment.

Bone marrow assessments include morphology (cytology), cytogenetics (cell culture and banding analyses), MRD via MFC, and biobanking for future analyses.

Efficacy will be evaluated during and at the end of each treatment cycle. PK will be assessed (at sites with appropriate capabilities) during the initial induction cycle. Safety will be monitored from the time of consent through 42 days after the start of the last treatment cycle (whether or not treatment is completed or discontinued early).

Long-Term Follow-up:

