Randomization ^a		X												
Cytarabine – continuous infusion		X	X	X	X	X	X ^d	X ^d						100 mg/m ² /day (Note: FLT3-positive participants may receive 200 mg/m ² /day)
Idarubicin 12 mg/m ² /day OR Daunorubicin 60 mg/m ² /day		X	X	X ^d										
Study intervention – bolus		X												4 mg/kg via IV push, begin 30 min after anthracycline infusion ends
Study intervention – continuous infusion		X	X	X	X	X	X ^d	X ^d						0.25 mg/kg/hour; Begin after bolus dose
Adverse event assessments	Procedure-related SAEs	All AEs ----- →										X	Record through 42 days after start of the last induction or consolidation treatment cycle (regardless of completion or discontinuation)	
Concomitant medications	X	----- →										X		
Medical resource utilization		----- →										X		

Abbreviations: AE=adverse event; aPTT=activated partial thromboplastin time; CR=complete response; D=day; D14=Day 14 (only day specified within window); DC=discontinuation; ECG=electrocardiogram; ECOG=Eastern Cooperative Oncology Group; FISH=fluorescence in situ hybridization; HMGB1=high mobility group box protein 1; MRD=measurable residual disease; MUGA=multigated acquisition scan; PK=pharmacokinetics; PT/INR=prothrombin time/international normalized ratio; SAE=serious adverse event

Refer to footnotes on the next page

^a All prestudy/screening procedures (including cytogenetic and molecular analyses) will ideally be completed within 14 days of randomization. First dose of study intervention should be administered as soon as possible after randomization, and must be administered no more than 24 hours after randomization. Screening procedures do not need to be repeated prior to reinduction.

^b Bone marrow aspirate/biopsy will be performed once between approximately Day 14 and Day 21 (Day 22-23 for participants taking midostaurin), when peripheral blood is negative for persistent AML, to determine the need for reinduction. (If the ~Day 14 bone marrow is not evaluable or assessment of aplasia is equivocal, a repeat evaluation may be performed 5 to 14 days later, at the discretion of the investigator, in order to determine effect and need for second induction). Thereafter, additional bone marrow samples will be collected to confirm response/persistence/relapse after second induction and consolidation cycles. For participants who achieve CR/CRi, measurable residual disease assays will be performed by the central laboratory on the recovery marrow sample.

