2.1. Study Rationale

The addition of dociparstat to standard 7+3 chemotherapy is expected to improve overall survival (OS) and relapse-free survival (RFS) versus chemotherapy alone, without additive toxicity. The current study is being conducted to confirm positive efficacy and safety results in previous studies of dociparstat for the treatment of AML and to show the benefits of adding dociparstat to standard 7+3 chemotherapy versus chemotherapy alone for the treatment of newly-diagnosed AML in adults.

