8.4.1. Time Period and Frequency for Collecting AE and SAE Information

Any SAE that is considered related to study procedures will be collected from the time of consent until the first dose of study intervention. Any other medical occurrences that begin during this time period will be recorded on the medical history/current medical conditions section of the eCRF (not as an AE/SAE).

All AEs will be collected from the time of first dose through 42 days after the start of the last treatment cycle with study intervention (i.e., dociparstat or placebo administered during initial induction, reinduction, or consolidation therapy as specified in this protocol).

All SAEs will be recorded and reported to the sponsor or designee immediately and under no circumstance should this exceed 24 hours, as indicated in [Appendix 2: Adverse Events](#). The investigator will submit any updated SAE data to the sponsor within 24 hours of the data being available.

Investigators are not obligated to actively seek new onset AEs or SAEs after the protocol-defined reporting period; however, if the investigator learns of any SAE and he/she considers the event to be reasonably related to the study intervention or study participation, the investigator must promptly notify the sponsor.

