9.5. Interim Analyses

Two interim analyses are planned.

The first interim analysis will be an early unblinded (only to the DMC) assessment of CR, CR with MRD_{neg}, and MRD_{neg}. This analysis will be reviewed by the DMC after 80 evaluable participants complete induction and reinduction (if applicable) assessments. Evaluable participants for this purpose are defined as those who either have a valid MRD result from the induction therapy recovery bone marrow (i.e., Day ~22 to 42), discontinue from induction therapy due to an AE or progressive disease, or die during induction therapy. The study will continue recruitment and enrollment while the interim analyses are being performed; a decision will be made as soon as practicable (targeted within 3 months) after the last participants' last assessments to be included in the analysis.

Three outcomes are possible from this analysis:

- The observed risk difference for CR is >30%, the observed risk difference for MRD_{neg} is >50%, or the combined total of observed risk differences for CR and CR with MRD_{neg} is >40%. The study will remain blinded and continue as planned.
- Observed risk differences for CR, MRD_{neg}, and CR with MRD_{neg} are all <5% The study will be unblinded to all parties and stopped.
- Criteria are not met for either of the preceding scenarios. The study will be unblinded to the sponsor, who, in consultation with the United States Food and Drug Administration, will determine whether to continue or stop the study. If the study continues, participants contributing to the interim assessment will not be used in subsequent inferential analyses and will be replaced. A summary of the data will be shared with investigators and ethics committees and publicly presented. Participants randomized after the interim cutoff and not contributing to the assessment will remain blinded and will contribute to subsequent inferential analyses.

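### Crude TEAE percentages over a participant-specific window could show a between-arm difference without any true toxicity difference, if the arms differ in the number of cycles received

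*Combined protocol and SAP*

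**What the plan says.** **Window.** Section 8.4.1 collects all AEs from first dose "through 42 days after the start of the last treatment cycle with study intervention". Section 9.4.4.1 counts TEAEs that begin "on or before 42 days after the start of the last cycle of study intervention". Section 8.4.5 (deaths reported as SAEs) and Section 8.3.4 (laboratory changes recorded as AEs) also refer to the last cycle of study intervention.

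**A different window elsewhere.** The synopsis monitors safety "through 42 days after the start of the last treatment cycle (whether or not treatment is completed or discontinued early". Table 1 (Section 1.2) records AEs through "42 days after start of the last induction or consolidation treatment cycle (regardless of completion or discontinuation", and Table 2 is to the same effect.

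**Cycles per participant.** Section 4.1 allows one induction cycle, a possible reinduction and up to four consolidation cycles, so 1 to 6 in all. Table 5 limits consolidation to participants in CR or CRi. Section 7.2 lists non-response after reinduction as a reason to stop study intervention. Section 6.3 has the investigator set the number of cycles by response, tolerability and suitability for alternatives such as transplant.

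**Summary.** Section 9.4.4.1 states: "Summaries (number and percent of participants) of TEAEs (by system organ class and preferred term) will be provided as follows". Section 9.4.4 contains no AE summary by cycle, by phase, over a fixed window or adjusted for exposure.

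**The concern.** AE observation time is itself an outcome after randomisation. A participant whose induction fails and who is not reinduced is observed for about 42 days. A responder who goes on to consolidation is observed through several further courses of myelosuppressive chemotherapy. Pooling both into one percentage mixes the drug's toxicity with the number of chemotherapy cycles received.

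Section 2.1 expects the drug to help "without additive toxicity", and the AE tables are the main evidence on that expectation. If one arm receives more cycles, its crude percentages rise for that reason alone. If study drug is permanently stopped more often in one arm while chemotherapy continues, that arm could contribute fewer AEs under the Section 8.4.1 and 9.4.4.1 wording, but not under the Table 1 wording.

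**Working it through.** **Inputs from the plan.** 1 to 6 cycles; consolidation requires CR or CRi; CR is planned at 50% in both groups (Section 9.2). The plan gives no AE rate or mean cycle count, so there is no stated safety figure to reproduce.

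**Assumptions, not in the plan.** The risk p of a first AE per cycle is the same in both arms, so there is no true toxicity difference. Each responder receives k consolidation cycles. Response here means CR/CRi, because that opens consolidation.

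**Length of the window.** With consolidation starts 28 to 42 days apart (assumed), a responder with four consolidation cycles and no reinduction is observed for 4×28 + 42 = 154 to 4×42 + 42 = 210 days, against 42 days for a non-responder without reinduction.

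**Formula.** With response rate c, and non-responders receiving m cycles,

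P(any AE) = (1 − c)·[1 − (1 − p)^m] + c·[1 − (1 − p)^(1+k)].

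This is linear in c, so

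false excess = (difference in c) × [(1 − p)^m − (1 − p)^(1+k)].

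**The plan's own assumption.** With 50% in both groups and the same k, the difference in c is 0 and the false excess is 0.0 points for every p and k.

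**Unequal response, p = 0.20, k = 3.** Responder risk is 1 − 0.8^4 = 0.5904.
- No reinduction (m = 1): non-responder risk is 0.20 and the gap 0.3904. Response of 50% vs 60% gives 39.5% vs 43.4% (3.9 points); 50% vs 80% gives 39.5% vs 51.2% (11.7 points).
- Every non-responder reinduced and no responder reinduced (m = 2): non-responder risk is 1 − 0.8^2 = 0.36 and the gap 0.2304. The excess is 2.3 points at +10 and 6.9 points at +30.

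**Sensitivity (m = 2 to m = 1).**

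| p | k | Responder risk | Gap, m=2 to m=1 | Excess at +10 | Excess at +30 |
|---|---|---|---|---|---|
| 0.10 | 2 | 0.271 | 0.081 to 0.171 | 0.8 to 1.7 | 2.4 to 5.1 |
| 0.20 | 3 | 0.590 | 0.230 to 0.390 | 2.3 to 3.9 | 6.9 to 11.7 |
| 0.30 | 4 | 0.832 | 0.322 to 0.532 | 3.2 to 5.3 | 9.7 to 16.0 |

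**Equal response, unequal consolidation.** Take 50% response in both arms, 25% reinduced regardless of response (assumed) and p = 0.20. The probability of no AE is 0.8 × (0.75 + 0.25×0.8) × (0.5 + 0.5×0.8^k) = 0.76 × (0.5 + 0.5×0.8^k). For k = 2 this is 0.623, so 37.7% have an AE; for k = 3 it is 0.575, so 42.5%. Transplant timing alone could therefore produce about 5 points.

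**Wording of the window.** For a participant who permanently stops study drug after induction but receives protocol consolidation, Sections 8.4.1, 8.4.5 and 9.4.4.1, read literally, end AE observation 42 days after the start of induction. The synopsis and Table 1 continue it to 42 days after the start of the last consolidation cycle. The two readings differ by every cycle given without study drug.

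**The case against.** A reader might infer that the crude percentages will show a toxicity difference even if none exists. The documents do not support that. It needs unequal cycle counts, whereas Section 9.2 plans on equal CR rates and Section 2.2 reports comparable CR/CRi in Phase 2b.

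Nor is the 30-point figure a planning assumption. The first-interim criterion ("The observed risk difference for CR is >30", in percentage points) is one of three alternative routes to continuing unchanged, is an observed value in 80 evaluable participants, and concerns CR. Consolidation opens on CR or CRi, so a gain made by turning CRi into CR adds no cycles. Reinduction also works the other way: with fewer non-responders there may be fewer reinductions, which is why the range above starts at 6.9 and not 11.7.

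A reader might also infer that a drug often stopped for aPTT would look safer. Frequent stopping is not supported. Sections 2.2 and 6.4 describe aPTT as normal for most participants and overlapping between groups, and under Section 7.1 an interrupted participant may receive study drug in the next cycle. Only permanent stopping ends the window. Section 6.1 defines a treatment cycle as including study intervention, so the two window wordings may have been meant to coincide.

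Other measures have their own windows: Day 30 and Day 60 mortality, and laboratory results by analysis window. Safety is mainly descriptive, the detailed SAP is deferred (Section 9.4) and not in the supplied text, and the format of the DMC tables is not stated.

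All of this stands as a limit on size and certainty. It does not give the AE tables a common observation period, and it leaves the conflicting wordings in place.

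**Conclusion.** The point holds as a conditional one. AE observation time depends on response and, on one reading, on stopping study drug, and the protocol specifies only crude percentages. A spurious difference could arise if the arms differ in response, transplant timing or permanent stopping of study drug. It is zero when cycle counts are equal. The direction is not fixed: the arm with more cycles shows more AEs.

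At an assumed 20% per-cycle risk and three consolidation cycles per responder, the false excess is about 2 to 4 points for a 10-point CR/CRi difference and about 7 to 12 for a 30-point one. These figures rest on a constant per-cycle risk equal in both arms, and on reinduction ranging from none to all non-responders. The absence of exposure adjustment is established for the protocol only. The conflict over the window is a matter of text and needs no assumption.

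**What to change.** Keep the overall percentages and add to Section 9.4.4.1:

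1. TEAE incidence in a fixed window for all treated participants, first dose to Day 42, not cut at reinduction, since a cut there would again make the window depend on response. This equalises scheduled observation time, though not the chemotherapy received within it. Either wording of the collection period already covers it.
2. Tables by phase (induction/reinduction, consolidation) with participants starting that phase as denominator, labelled descriptive because the consolidation group is selected after randomisation.
3. Exposure-adjusted rates for AEs of special interest and for Grade 3 or higher, serious and fatal TEAEs, with cycles received by arm. The phase tables are still needed, because one overall rate can mix different induction and consolidation risks.

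Separately, reconcile Sections 8.3.4, 8.4.1, 8.4.5 and 9.4.4.1 with the synopsis and Tables 1 and 2, so that AE observation does not depend on whether study drug was stopped while protocol chemotherapy continued.

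The cost is protocol and SAP wording, a few extra tables from dates already collected, and slightly longer AE collection in some participants. Section 9.4 has the SAP finalised before the first interim analysis, which is the natural point to add the tables.

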9.4.4.2. Laboratory Results

Descriptive statistics (N, mean, standard deviation, median, Q1, Q3, minimum, and maximum) will be provided for each continuous laboratory test as follows:

- Baseline values
- Values at each postbaseline analysis window (to be defined in the SAP)
- Change from baseline at each postbaseline analysis window

The minimum, maximum, and last postbaseline value / change from baseline will also be summarized. Missing data will not be imputed.

Laboratory tests will be descriptively analyzed by grade and analysis window using counts and percentages. The maximum and last postbaseline grade for each participant will also be summarized. Denominators will be the number of participants with a graded (or normal) test during the window. Laboratory tests with criteria for both increased and decreased levels will be analyzed for each direction (i.e., increased and decreased). This analysis will be generated twice to count (1) treatment-emergent increases in laboratory grades (i.e., only those above the baseline grade) and (2) any grade regardless of baseline.

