1.2. Schedule of Activities

Table 1: Schedule of Activities/Assessments: Induction Cycle and Reinduction Cycle (as applicable)

Study Day:	Screen ^a	BL/ D1	D 2	D 3	D 4	D 5	D 6	D 7	D 8	D 14- 21	D22 until count recovery or Day 42 ^c	Post-CR	Early Therapy DC	Notes
Examination / Procedure														Study day is relative to start of each treatment cycle
Informed consent	X													
Eligibility criteria	X	X												
Demographics	X													
Medical history	X	X												
ECOG status (induction only)	X	X												
Physical exam and vital signs	X													Predose findings=medical history; Findings after first dose=AE
Height / Weight	X													
ECG (induction only)	X	X							X					D1: Before and after bolus dose; D8: At the end of infusion
Echocardiogram / MUGA scan	X													Repeat per standard of care.
Pregnancy test (as applicable)		X												Women of childbearing potential
Peripheral blood samples:														
– Molecular genetics (central)	X													
– Immunophenotyping (central)	X													
– FISH (central)	X													
– Fibrinogen, D-dimer (local)	X													
– Clinical chemistry (local)	X	X	X		X		X		X	D14				
– Hematology (local)	X	X	X		X		X		X	X	X			Every other day through recovery.
– PT/INR, aPTTe,f (local)	X	X ^f	X	X	X	X	X	X	X	D14				Do not draw from the same line used for drug administration ^e
– PK blood samples ^e (central) (induction only) (at sites with appropriate capabilities)		X			X				X					(±10min) D1: predose, end of bolus, and 1 and 12 hours after bolus; D4: morning; D8: end of infusion, and 0.5, 1, 2, and 4 hours after end of infusion
– HMGB1 ^{e,g} (central)		X			X				X	D14	At recovery ^{b,c}			
– Biobanking (central)	X										X ^c			Optional, per local regulation/approval

Consolidation Therapy, as applicable – see Table 2

Study Day:	Screen ^a	BL/ D1	D 2	D 3	D 4	D 5	D 6	D 7	D 8	D 14- 21	D22 until count recovery or Day 42 ^c	Post-CR	Early Therapy DC	Notes
Examination / Procedure													Study day is relative to start of each treatment cycle	
Bone marrow aspirate/ biopsy:														
– MRD analyses (central)	X										At recovery ^{b,c}			Required. Use first draw of marrow.
– Biobanking (central)	X										At recovery ^{b,c}			Optional, per local regulation/approval
– Morphology (local)	X									X ^b	At recovery ^{b,c}			
– Cytogenetics (local)	X													
Buccal swab or saliva specimen (central) (induction only)											X			Optional, single sample for germ line analysis

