^c Count recovery is defined as an absolute neutrophil count >1000/ μ L and a platelet count >100,000/ μ L. If count recovery occurs, perform bone marrow aspirate/biopsy within 7 days. If count recovery has not occurred by ~Day 36 after induction or reinduction, perform a bone marrow aspirate/biopsy on or before Day 42 to evaluate disease status.

^d Participants who do not achieve leukemia-free state (<5% bone marrow blasts) on bone marrow aspirate performed between ~Days 14-21 (Day 22-23 for participants taking midostaurin) may receive a reinduction cycle. Participants 18 to 59 years will receive the same 7+3 regimen; participants \geq 60 years will receive a modified “5+2” regimen, with cytarabine and study intervention administered on Days 1 through 5 and idarubicin/daunorubicin on Days 1 and 2.

^e Do not draw blood (especially for aPTT or PK analyses) from the same line that is used for study intervention administration. Drawing blood from a heparinized line may falsely alter results obtained; if using an indwelling catheter, draw ~5 mL of blood from the line for discard before drawing the aPTT and PK samples.

^f Draw blood for aPTT measurements no sooner than 8 hours after the bolus dose. During the continuous infusion, measure aPTT daily.

^g Refer to laboratory manual for instructions on obtaining a separate sample for HMGB1 analyses versus using a biobanked sample.

Note: All participants will be followed-up for long-term outcomes for 5 years after randomization. See Section [8.2.3](#).

Table 2: Schedule of Activities/Assessments: Consolidation Cycles

Study Day: Examination / Procedure	D1	D2	D3	D4	D5	D6	D14	D7 until count recovery or D42 ^h	Follow-up	Notes
Weight	X									Day is relative to start of each treatment cycle
Bone marrow aspirate/ biopsy:										After each consolidation cycle and to confirm response/ relapse/ persistent disease
–Morphology (local)								X – at recovery		
–MRD analyses (central)								X – at recovery		After each consolidation cycle
–Biobanking (central)								X – at recovery		Optional, per local regulations/approvals
Peripheral blood samples:										
–Hematology (local)	X	X		X		X	X	X		Every other day through recovery
–Clinical chemistry (local)	X	X		X		X	X			
–PT/INR, aPTT ^{i,j} (local)	X	X	X	X	X	X	X			
–HMGB1 ^{g,i} (central)	X							X – at recovery		
–Biobanking (central)								X – at recovery		

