
 To assess the safety and tolerability of dociparstat plus chemotherapy versus chemotherapy alone for the treatment of newly-diagnosed AML. 	
 Incidence of AEs: overall, treatment-related, Grade 3 or higher in severity, serious, fatal, and those resulting in treatment discontinuation. Incidence of AEs of special interest. Change from baseline in clinical laboratory parameters. Distribution of graded clinical laboratory results. Proportion of participants who meet defined QT/QTc criteria. Incidence of mortality at Day 30 and Day 60.

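### Late-cycle hematology tables are selected on the outcome: tests stop once both lineages recover, yet each window counts only participants tested in it

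*Combined protocol and SAP*

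**What the plan says.** **Schedule (Section 1.2).** In Table 1 (induction and reinduction) the last hematology column is "D22 until count recovery or Day 42", with the note "Every other day through recovery". In Table 2 (consolidation) the corresponding column is "D7 until count recovery or D42". The table footnotes set the stopping rule: "Count recovery is defined as an absolute neutrophil count" above 1000/µL together with a platelet count above 100,000/µL. Both lineages must recover before scheduled testing ends.

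**Analysis (Section 9.4.4.2).** Values, changes from baseline and grades are summarised at each postbaseline window. Window definitions are left to the SAP. For grades, "Denominators will be the number of participants with a graded (or normal) test during the window". For the continuous summaries, "Missing data will not be imputed". Nothing is said about a participant who has no test in a window because counts had already recovered. The section also reports the maximum and last postbaseline grade per participant.

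**Endpoint (Section 3).** The safety endpoints include change from baseline in laboratory parameters and "Distribution of graded clinical laboratory results".

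**The concern.** How long a participant is tested depends on the quantity being tabulated. A participant who recovers on Day 27 has a known, favourable status in Days 29-35, but contributes nothing to that window. One who has not recovered contributes throughout. The late windows are therefore not a comparison of the randomized groups.

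Different recovery speeds by arm are plausible on the protocol's own reasoning. Section 2.2 links dociparstat, through platelet factor 4, to platelet recovery after chemotherapy. If the arms recover at different speeds, they lose different fractions of their participants from the late windows. A reader of the safety tables could then see a cytopenia difference of the wrong size, or one in a lineage that the drug does not affect.

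**Working it through.** The plan states no cytopenia rate, recovery time or window, so there is no figure to reproduce. The check is an identity, followed by an illustration.

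**Identity.** Let *p* be the proportion of all participants in an arm with ANC ≤1000/µL on the last scheduled test day of a window, and *s* the proportion tested at all in that window. A participant with ANC ≤1000 has not met count recovery and so is still being tested. The numerator is the same under either denominator, and the tested-only percentage is *p/s*. The same holds for platelets ≤100,000/µL. Two results follow:

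- *s* < 1 in late windows, so the percentage is inflated in both arms.
- Ratio shown = true ratio × (*s* control / *s* dociparstat). Because *s* depends on both lineages, an effect on one lineage changes the table for the other.

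**Illustration.** From the documents: testing ends when both thresholds are met, and tests are every other day from Day 22. Assumed: lognormal recovery times with log-SD 0.25, correlation 0.5 between lineages, 7-day windows, no deaths, reinduction or unscheduled tests; 400,000 simulated participants per arm. Median recovery days are also assumed. All percentages are control vs dociparstat.

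| Scenario (median days) | Window, measure | Tested share *s* | All participants | Tested only |
|---|---|---|---|---|
| A. Both lineages slower (28 vs 32) | D29-35, ANC | 0.67 vs 0.85 | 21.8% vs 40.4% (+18.6) | 32.7% vs 47.7% (+15.0) |
| A | D36-42, ANC | 0.34 vs 0.57 | 5.2% vs 13.7% (+8.5) | 15.4% vs 24.2% (+8.8) |
| B. ANC only slower (28 vs 32; platelets 30) | D36-42, ANC | 0.40 vs 0.51 | 5.2% vs 13.8% (+8.6) | 13.0% vs 26.9% (+13.9) |
| B | D36-42, platelets | 0.40 vs 0.51 | 8.9% vs 9.0% (+0.1) | 22.3% vs 17.4% (-4.9) |
| C. Platelets only faster (32 vs 27; ANC 28) | D36-42, ANC | 0.47 vs 0.31 | 5.3% vs 5.2% (0.0) | 11.1% vs 16.8% (+5.7) |
| C | D36-42, platelets | 0.47 vs 0.31 | 13.8% vs 3.9% (-9.9) | 29.2% vs 12.4% (-16.8) |
| D. No difference (ANC 28, platelets 30) | D36-42, ANC | 0.40 vs 0.40 | 5.3% vs 5.2% (0.0) | 13.0% vs 13.0% (0.0) |

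Differences are taken before rounding.

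**Identity against the table, Days 36-42, ANC.** Scenario A: 2.63 × 0.34/0.57 = 1.57, the simulated tested-only ratio. Scenario C: 1.00 × 0.47/0.31 = 1.52, against 1.51 simulated.

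**Reading.** Every tested-only percentage exceeds its all-participant counterpart. For the affected lineage the ratio moves towards 1 (A: 2.63 to 1.57; B: 2.67 to 2.07; C: 0.28 to 0.43), but the risk difference shrinks in A at Days 29-35, barely changes in A at Days 36-42, and grows in B and C. For the unaffected lineage a difference appears from nothing. With equal recovery in both lineages, no false difference appears.

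**The case against.** The strongest reply is that this touches little that matters. Section 9.4.4 makes safety analyses generally descriptive, and no decision rule uses these tables. Count recovery is compared elsewhere with a sound denominator: time to neutrophil and platelet recovery is defined for all participants (Table 7) and tested in fixed sequence (Section 9.4.3), prolonged neutropenia and thrombocytopenia past Day 42 are endpoints (Section 3), and prolonged Grade 4 neutropenia is an adverse event of special interest (Section 8.4.7). Maximum grade does not depend on late windows. All of this stands, and it sets the severity. It does not repair the by-window tables, and time to recovery covers only induction and reinduction, not consolidation.

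Second, the windows are not yet defined, and Section 2.2 reports that dociparstat did not prolong count recovery in Phase 2b. That stands as to size: windows, recovery times and arm shifts are assumptions here, and without a true difference in recovery no false one appears. But the protocol has already fixed the denominator, and the inflation within each arm remains.

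Third, testing need not end at recovery. Section 8.3.4 allows additional tests, and hematology is repeated on Day 1 of each consolidation cycle. Such tests would return some recovered participants to the windows, but at the discretion of sites or only for those who continue treatment.

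A reader might also infer that the tables always understate a between-arm difference, and hence hide harm if dociparstat slows recovery. A model with one recovery time per participant suggests this: with normal recovery times (SD 6 days, means Day 32 control and Day 35 dociparstat), the share with any below-recovery count in Days 29-35 is 84% vs 91% among those tested, but 63% vs 80% among all. The documents do not support the general claim. Stopping requires both lineages, and scenarios B and C then show overstated and spurious differences.

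**Conclusion.** The selection follows directly from the stated schedule and the stated denominator. Late-cycle hematology windows overstate cytopenia in both arms. When recovery speed differs by arm, the difference they show can be too small, too large or false. In the illustration, 31% to 57% of participants are still tested in Days 36-42, and the errors in the risk difference in that window run from 0.3 points (scenario A, ANC) to 6.9 points (scenario C, platelets: 16.8 - 9.9). These sizes rest on assumed recovery times and windows and ignore deaths, reinduction and unscheduled tests.

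The consequence is limited to descriptive by-window hematology summaries. It would be wrong to infer that the plan as a whole conceals delayed recovery, since the analyses designed to detect it do not use this denominator. Severity: low.

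**What to change.** In Section 9.4.4.2 and the SAP, for ANC and platelet windows after Day 21 of induction or reinduction and after Day 14 of consolidation:

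- Report grades over all participants who started that cycle and were alive at the start of the window. Keep in the denominator those who recovered and moved on to a next cycle or other AML therapy; otherwise the selection returns.
- Put participants whose scheduled testing ended at documented count recovery in a separate row, such as 'recovered, testing ended', rather than assigning them a grade. Show the number actually tested.
- Limit by-window means and changes from baseline for hematology to the fixed-day visits.
- Keep the observed-only tables as a supplement, and refer to the time-to-recovery analysis for the between-arm comparison in induction and reinduction.

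Clinical chemistry is scheduled on fixed days and needs no change. The cost is wording and modest programming, with no new data. The downside is that a late fall in counts after recovery, with no recorded test, is not seen.
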